8.1.4 Drug Accountability

Under Title 21 of the Code of Federal Regulations (21CFR §312.62) the investigator is required to maintain adequate records of the disposition of the investigational agent, including the date and quantity of the drug received, to whom the drug was dispensed (participant-by-participant accounting), and a detailed accounting of any drug accidentally or deliberately destroyed.

Records for receipt, storage, use, and disposition will be maintained by the study site. A drugdispensing log will be kept current for each participant. This log will contain the identification of each participant and the date and quantity of drug dispensed. All records regarding the disposition of the NULOJIX® will be available for inspection by the clinical trial monitor.

8.2 Induction and Maintenance Immunosuppression Medications

The following induction and maintenance immunosuppression medications are considered standard of care post-transplantation and will be supplied by the hospital pharmacy; Medrol® (methylprednisolone), Thymoglobulin® (Anti-Thymocyte Globulin- Rabbit), Mycophenolate Acid, and Prograf® (tacrolimus). Please refer to applicable product labeling for preparation and administration instructions and well as known and potential risks.

8.3 Concomitant Medications

Concomitant medications should be administered according to each centers standard of care. The centers will record immunosuppressive and non-immunosuppressive therapy information on an eCRF in the study electronic data capture system.

8.4 Prophylactic Medications

8.4.1 Viral Prophylaxis

CMV Sero Positive Donor and Sero Positive Recipient (D+/R+)

When tolerating PO or at discharge, subjects will receive Valganciclovir (Valcyte®) PO, 900 mg every day. Dose adjusted according to renal function. Treatment is to continue for 85 days post-transplant for the prevention of CMV.

CMV Sero Positive Donor and Sero Negative Recipient (D+/R-)

When tolerating PO or at discharge, subjects will receive Valganciclovir (Valcyte®) PO, 900 mg QD. Dose adjusted according to renal function. Treatment is to continue for 24 weeks post-transplant for the prevention of CMV.

CMV Sero Negative Donor and Sero Positive Recipient (D-/R+)

When tolerating PO or at discharge, subjects will receive Valganciclovir (Valcyte®) PO, 900 mg QD. Dose adjusted according to renal function. Treatment is to continue for 85 days post-transplant for the prevention of CMV.

CMV Sero Negative Recipient and Negative Donor (D-/R-)

When tolerating PO or at discharge, subjects will receive Valacyclovir (Valtrex®), 1000 mg PO BID. Dose adjusted according to renal function. Treatment is to continue for 85 days post-transplant for the prevention of HSV and VZV.

8.4.2 PCP Prophylaxis

Any of following regimens, at the discretion of the treating medical team, are acceptable for PCP prophylaxis, starting on post-operative day one or when subject is taking oral medications and continuing until 1 year post transplant or later based on your institutional standard of care.

Bactrim [™]/Septra [®] (Trimethoprim-sulfamethoxazole) single strength (SS; 80/400) administered once daily, if GFR >30. If GFR ≤30), single strength administered once a day on every Monday, Wednesday, and Friday. If patient is on hemodialysis, single strength administered on the day of dialysis after dialysis sessions.

For participants allergic to or intolerant of sulfa compounds or trimethoprim-sulfmethoxazole therapy, and if G6PD level is normal, Aczone ® (Dapsone) 100 mg PO once daily.

For participants allergic to or intolerant of sulfa compounds or trimethoprim-sulfmethoxazole therapy, and is G6PD deficient, Mepron® (Atovaquone) 1500 mg once daily.

8.5 Management of Rejection or Graft Loss

Management of rejection or graft loss is defined by each centers standard of care. The centers will record the treatment information on an eCRF in the study electronic data capture system. Any subject who experiences rejection or graft loss following week 52 will continue to follow the schedule outlined in Appendix 3 [Schedule of Events (Recipient) Post-Transplant (Year 2)].

If a subject experiences rejection either during or after tacrolimus withdrawal, they will complete the remaining visits in Appendix 2 (Schedule of Events (Recipient) Year 1) and continue to be followed based on Appendix 3 [Schedule of Events (Recipient) Post-Transplant (Year 2)].

8.6 Prohibited Medications

Prohibited medications for this protocol, except as specifically indicated in this protocol include:

- Steroid medication (save topicals and prednisone at a dose of ≤ 5 mg daily, or an equivalent dose of hydrocortisone, for physiological replacement only)
- Other investigational products
- Other immunosuppressive agents not defined in the protocol.
- Live vaccines

8.7 Modification or Discontinuation of Study Therapy

Study treatment may be prematurely discontinued at the discretion of the Investigator for any of the following reasons:

- 1. The subject is unwilling or unable to comply with the protocol.
- 2. The subject experiences graft failure.
- 3. Any clinical AE, laboratory abnormality or intercurrent illness, which in the opinion of the site PI indicates that continued treatment with study therapy is not in the best interest.
- 4. Pregnancy.
- 5. Two consecutive missed NULOJIX® (Belatacept) infusions.

Subjects who prematurely discontinue study treatment will be treated according to the site standard of care and followed until 52 weeks post-transplant. Please refer to Reduced Follow-Up Schedule (Appendix 4). If subjects discontinue study therapy beyond week 52, they will complete the visits outlined in Appendix 3 [Schedule of Events (Recipient) Post-Transplant (Year 2)]. If the subject is unable to return to the study center, the data associated with these visits may be obtained from the subject's local physician.

9 CRITERIA FOR PREMATURE TERMINATION OF THE STUDY

9.1 Participant Withdrawal Criteria

Participants may be prematurely terminated from study for the following reasons:

- 1. The subject elects to withdraw consent from all future study activities, including follow-up.
- 2. The participant is "lost to follow-up" (i.e., attempts to reestablish contact have failed).
- 3. The participant develops a clinical AE, laboratory abnormality, or intercurrent illness or any other event which, in the opinion of the investigator, indicates that continued treatment with study therapy and further participation in the study (including obtaining vital status of the participant and renal graft) is not in the best interest of the participant.
- 4. The participant dies.
- 5. The participant is found to be TB positive.

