Graft Failure- Renal	90 consecutive days of dialysis dependency.				
Graft Failure-	Return to exogenous insulin therapy or initiation of oral hypoglycemic agents for greater				
Pancreas	than 30 days.				
Insulin	Insulin free.				
Independent					
Premature	A subject will be terminated prematurely from the study if: 1) the subject withdraws consent,				
Termination	2) is lost to follow-up, 3) the investigator or sponsor decision, 4) death, or 5) the subject is				
	found to have a positive TB test.				
Protocol Mandated	Any procedure performed solely for the purpose of this research study, not considered site				
Procedures	specific standard of care.				
Randomized	A subject who met all eligibility criteria; met with the study investigator or designee to				
	discuss the study purpose, requirements (i.e., time requirements, schedule of events, etc.),				
	discussed all risks and benefits, signed the informed consent document and was randomly				
	assigned to one of the two treatment groups.				
Reduced Follow Up	Randomized subjects who are no longer following the assigned study therapy regimen, and				
r i	do not meet the criteria for early termination, will continue to participate in the study for				
1	safety and applicable enupoint assessments.				
Renal Dysfunction	safety and applicable endpoint assessments. Two consecutive readings with an increase in serum creatinine of 25% from baseline.				

Clinical Trials in Organ Transplantation (CTOT) CONFIDENTIAL Protocol CTOT-15

Sensitizing Event	Defined as a blood transfusion, pregnancy, or an event in the opinion of the Investigator		
	would necessitate repeating the PRA.		
Treated Diabetes	Receipt of any oral medication or insulin for the treatment of diabetes for >14 days		
Tuberculosis	TB is defined as a positive TB Skin Test (TST/PPD) or a TB-specific interferon gamma release assay, such as a QuantiFERON®-TB, QuantiFERON®-TB in tube, or a T-Spot®.		
Withdrawn from Study Therapy	Subjects who prematurely discontinue study treatment will be treated according to the site specific standard of care and followed for safety until 52 weeks post-transplant.		
Primary Nonfunction (PNF)	Graft failure that occurs between 3 and 7 days post-transplant.		

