13.2 Endpoint Assessments

13.2.1 Primary Clinical Endpoint

The primary endpoint will be the week-52 eGFR. Mean eGFR of the belatacept group will be compared to the mean eGFR of the tacrolimus reference group within a mixed models repeated measures (MMRM) framework , wherein repeated measures of eGFR at weeks 4, 12, 28, 36 and 52 will be modeled as a linear function of time (and perhaps other baseline covariates) in the 2 treatment groups. At week-52, a contrast will be made between the eGFR mean of the belatacept group and the eGFR mean of the tacrolimus group. ANCOVA assumptions will be evaluated graphically via standard residual analyses. If the assumptions fail, a suitable transformation (e.g., natural logarithms) will be found and the data will be reanalyzed on the transformed scale. Results will be reported with p-values associated with the F-test for each contrast and the corresponding mean treatment differences with two-sided 95% confidence intervals. All tests of significance will be two-tailed at the 0.05 level.

Estimating the contrasts within the repeated measures framework will provide treatment comparisons that are robust to subject dropout bias as long as the dropout pattern is missing at random²⁷. Data are missing at random whenever the "missingness" mechanism is a function of observable relationships among the nonmissing responses and covariates. Using the methods of Ma et al.²⁸, we will evaluate the MAR assumption in the data prior to implementing the MMRM analysis. If the MAR assumption fails, we will consider more robust alternatives (e.g., pattern mixture modeling)²⁹.

A number of studies have shown RMANCOVA to be superior to analyses of completers or of data with LOCF imputations³⁰. Nonetheless, we will conduct 2 related sensitivity analyses: (1) replace the missing week-52 values with the corresponding nonmissing week 36 values of each subject, dropping anyone who is missing both week-36 and week-52 and perform the ANCOVA as currently specified; (2) include only the completers in the ANCOVA analysis (i.e., exclude all dropouts). The sensitivity analyses will be included as additional secondary analyses.

13.2.2 Secondary Clinical Endpoints

The secondary endpoints are defined in Protocol section 1.5.

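### Section 9.1 item 3 lets an investigator stop collection of vital and renal graft status because a subject is ill, and the Study Definitions let it take precedence over the reduced follow-up in 8.7

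*Combined protocol and SAP*

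**What the plan says.** Three parts of the protocol decide what happens to a subject who becomes ill on study.

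- **Section 8.7, item 3** allows study treatment to be stopped for "Any clinical AE, laboratory abnormality or intercurrent illness, which in the opinion of the site PI indicates that continued treatment with study therapy" would not serve the subject's interest. The consequence is stated: "Subjects who prematurely discontinue study treatment will be treated according to the site standard of care and followed until 52 weeks post-transplant". Appendix 4 then schedules serum creatinine and assessment of graft loss and death. Section 8.7 adds that visit data may come from the local physician if the subject cannot return.
- **Section 9.1, item 3** allows termination from the study itself. Its trigger reads "The participant develops a clinical AE, laboratory abnormality, or intercurrent illness or any other event which, in the opinion of the investigator", and it applies when, besides continued treatment, "further participation in the study (including obtaining vital status of the participant and renal graft) is not in the best interest of the participant".
- **Study Definitions.** Reduced Follow Up covers randomised subjects off their assigned regimen who "do not meet the criteria for early termination, will continue to participate in the study for" safety and applicable endpoints. The reasons for Premature Termination include "3) the investigator or sponsor decision", with no qualification.

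Section 11.4.1 keeps adverse-event collection open for 30 days after a subject withdraws without withdrawing consent, or is withdrawn. Section 13.2.1 describes the primary comparison of week-52 eGFR as "robust to subject dropout bias as long as the dropout pattern is missing at random".

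**The concern.** The same kinds of event lead either to follow-up through week 52 or to no outcome collection beyond 30 days of adverse events. What separates the two is an investigator's opinion about participation, for which the protocol gives no criterion. The trial is open-label, and section 10.4.1 itself records concern that unblinded investigators may be biased in assessing endpoints.

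Three results depend on what is lost:

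- the week-52 eGFR, which is the primary endpoint;
- the safety outcome of death, graft loss or undetectable c-peptide (1.5.5);
- the stopping rule for graft loss due to rejection (9.2.2), which counts losses among all randomised subjects. An unseen loss drops out of the numerator while the subject stays in the denominator.

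Item 3 names only the renal graft, but ending participation ends pancreas follow-up too.

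**Working it through.** **1. The two rules side by side.**

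| | 8.7 item 3 | 9.1 item 3 |
|---|---|---|
| Events | clinical AE, laboratory abnormality, intercurrent illness | the same three, plus any other event |
| Judgement | treatment not in the subject's interest | treatment and participation not in the subject's interest |
| Criterion for the judgement | none | none |
| Follow-up | to week 52, Appendix 4 | ends; vital and renal graft status expressly included |
| What remains | creatinine, graft loss, death | AE collection for 30 days (11.4.1) |

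Reduced follow-up is defined by not meeting the termination criteria. A subject who satisfies both rules is therefore governed by 9.1.

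**2. The plan's own figures.** Table 11 (30 per arm, 80% power, two-sided) gives detectable differences of 12.0, 15.0 and 18.0 at alpha 0.05 for SD 16, 20 and 24. Solving the two-sample t-test (58 df) gives 11.77, 14.71 and 17.65, which round up to the stated values at the next 0.5. No dropout allowance is stated.

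**3. Raw bias (assumed inputs).** The documents give no termination rate. Suppose L of 30 subjects in one arm are lost, with mean week-52 eGFR lower by D than those retained. The retained mean is then too high by (L/30) × D.

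- L = 1, D = 10: 1/30 × 10 = 0.33 mL/min
- L = 3, D = 25: 3/30 × 25 = 2.5 mL/min

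Against Table 11, 2.5 is 21% of 12.0, 17% of 15.0 and 14% of 18.0.

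**4. Bias in the planned model (assumed inputs).** The repeated-measures model also uses eGFR at weeks 4, 12, 28 and 36. Suppose the whole deficit is already visible at the last observed visit, with equal variances and within-subject correlation r. The unrecovered part is then roughly (L/30) × D × (1 − r). For L = 3 and D = 25:

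- r = 0.5: 2.5 × 0.5 = 1.25 mL/min
- r = 0.9: 2.5 × 0.1 = 0.25 mL/min

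If no earlier visit shows the decline, the figure stays near 2.5.

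**5. Precision (assumed loss).** At SD 20 and a difference of 15.0, power is 81.5% with 30 per arm and 79.3% if 3 are lost from one arm. This is a minor effect.

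**6. Stopping rule.** Exact one-sided 95% lower limits reproduce Table 5. With 40 randomised, 13 losses give 20.41% and meet the 20% rule, while 12 give 18.31% and do not. With 60 randomised, 18 give 20.37% and 17 give 18.93%.

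**The case against.** The strongest reply is that the two rules do not apply the same test. Item 3 of 9.1 needs a second finding, that participation itself is against the subject's interest. The parenthesis could be read as a high bar: if looking up vital status is harmless, the item is not met and 8.7 applies. The distinction stands, and a subject stopped under 8.7 is not automatically terminated. It does not settle the matter, because the bar has no criterion and the Premature Termination definition contains no such test.

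The reply is also right about several stronger inferences that a reader might draw:

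- **That missing at random fails.** Termination after a recorded eGFR decline can be missing at random. The assumption breaks only if termination depends on what was not recorded. Section 13.2.1 plans a check and names pattern-mixture modelling as something to consider. However, observed data cannot confirm the assumption, and the two fixed sensitivity analyses (week-36 carry-forward and completers only) do not recover these outcomes.
- **That 2.5 mL/min is the bias of the primary analysis.** It is the bias of a raw retained mean, at the top of an assumed range.
- **That item 3 affects many more subjects than the TB criterion in item 5.** The documents give a rate for neither, and termination is permitted, not required.
- **That one unseen loss at 18 of 60 would leave enrollment running.** At 60 randomised, accrual is complete and only the DSMB review is at stake. Some integer boundary exists in any such rule, only rejection-related losses count, and losses before termination are already counted.

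Finally, Version 7.0 is dated June 28, 2016, and study completion is August 31, 2016, so the gain at this stage is limited.

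**Conclusion.** The point holds as a flaw in a stated rule. The protocol permits illness to end collection of the primary endpoint and of death and graft-loss status, on an uncriterioned judgement by an unblinded investigator. This puts the missing-at-random assumption at risk and can under-count both the safety outcome and the graft-loss stopping rule.

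The size cannot be computed from the documents. With 1 to 3 of 30 lost in one arm and a deficit of 10 to 25 mL/min, both assumed, the raw retained mean is overstated by about 0.3 to 2.5 mL/min. The model-based bias is smaller where earlier visits show the decline. A reader might infer that the primary result is biased. The documents do not support that: they show that the loss is allowed, not that it occurred. The change is still worth making, because the loss is avoidable and each arm has only 30 subjects.

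**What to change.** Reconcile the Study Definitions (Premature Termination and Reduced Follow Up), section 8.7 and section 9.1:

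- Delete the parenthesis in 9.1 item 3.
- State that when an investigator or the sponsor ends study therapy, or study visits and sampling, the following are still collected for every randomised subject: vital status, kidney and pancreas graft status, and any week-52 serum creatinine available from routine care or the local physician.
- Make withdrawal of consent for follow-up the only exception to that collection.
- Align the investigator-or-sponsor-decision entry in the Premature Termination definition with this.

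The investigator's discretion to stop treatment, visits or sampling is unchanged. The cost is wording changes and a record check on a few subjects, with no extra visit. At this late stage the record check on subjects already terminated under item 3 is the part that would still recover data, where their consent for follow-up stands.

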9.2 Study Stopping Rules

9.2.1 Protocol Suspension and Review

Study enrollment at all participating sites will be suspended pending expedited review of all pertinent data by the institutional review board (IRB), the National Institute of Allergy and Infectious Diseases (NIAID), and the NIAID Data Safety Monitoring Board (DSMB), if any one of the following occurs:

- 1. Any unexpected fatal or life-threatening AE that is possibly, probably, or definitely related to the study treatment regimen (Section 8);
- 2. Any event(s) which in the opinion of the Medical Monitor or Protocol Chair indicates the need for DSMB review;
- 3. Any instance of progressive multifocal leukoencephalopathy (PML).

In the event of any participant death, the study will pause for review of the event by the medical monitor and the protocol chair. Any death that is not clearly due to non-study causes will result in a continued pause in enrollment and DSMB review. "Non-study causes" will include events such as deaths due to motor vehicle accidents.

9.2.2 Continuous Monitoring of Specific Events

In addition, the incidence of specific safety-related events of particular concern will be continuously monitored in each treatment arm throughout the study to determine if any of their observed subjectbased incidence rates exceed a threshold incidence rate of concern pre-specified for each particular event. However, since little is known about what incidence rate to expect for graft loss of either pancreas or kidney due to acute or chronic rejection, that rule is based on the incidence of rejection events involving one or both allografts in all subjects randomized.

The following events will be evaluated within each treatment arm, except as noted, and the corresponding thresholds of concern are:

- 1. Biopsy-proven acute rejection (BPAR) in either pancreas or kidney above 25%.
- 2. Pancreas rejection above 20%.
- 3. Post-Transplant Lymphoproliferative Disease (PTLD) above 2% at any time.
- 4. Incidence of graft loss of either organ due to any rejection above 20% in all randomized subjects.

These rules will be implemented by the SACCC, and continuously monitor the occurrence of any of these events. If any stopping rule is met, enrollment and randomization will be halted pending expedited DSMB review.

The stopping rules for BPAR and PTLD will be considered to be met if the lower one-sided 95% exact confidence limit on the observed incidence rate exceeds the corresponding threshold level of concern for that event. The following two tables describe the minimum numbers of events (n) out of selected numbers of subjects randomized within each treatment arm (N) which, if equaled or exceeded, would satisfy the stopping rule for BPAR and PTLD.

Number of	Number of Subjects	Observed	Lower 95%
Subjects with	Randomized (N) in Either	Incidence Rate	Confidence Limit
Event (n)	Arm	(%)	(%)
4	5	80.00	34.26
6	10	60.00	30.35
8	15	53.33	30.00
9	20	45.00	25.87
11	25	44.00	26.99
13	30	43.33	27.87

Table 2: Minimum Numbers of Subjects with Events that Meet the Stopping Rule for BPAR
in Either Organ in Either Treatment Arm Using a Threshold of 25%

Table 3: Minimum Numbers of Subjects with Events that Meet the Stopping Rule for
Pancreas Rejection in Either Treatment Arm Using a Threshold of 20%

Number of Subjects with Event (n)	Number of Subjects Randomized (N)	Observed Incidence Rate (%)	Lower 95% Confidence Limit (%)
4	5	80.00	34.26
5	10	50.00	22.24
7	15	46.67	24.37
8	20	40.00	21.71
9	25	36.00	20.24
11	30	36.67	22.11

Table 4: Minimum Numbers of Subjects with Events that Meet the Stopping Rule for PTLD in Either Treatment Arm Using a Threshold of 2%

Number of Subjects with Event (n)	Number of Subjects Randomized (N) in Either Arm	Observed Incidence Rate (%)	Lower 95% Confidence Limit (%)
2	5	40.00	7.64
2	10	20.00	3.68
2	15	13.33	2.42
3	20	15.00	4.22
3	25	12.00	3.35
3	30	10.00	2.78

The stopping rule for graft loss of either organ due to any rejection will be considered to be met if the lower one-sided 95% exact confidence limit on the observed incidence rate among all study subjects is greater than 20% at any time during the study.

Table 5: Minimum Numbers of Subjects with Events that Meet the Stopping Rule for GRAFT LOSS in All Subjects Randomized at Any Time Using a Threshold of 20%

Number of Subjects with Event (n)	Number of Subjects Randomized (N)	Observed Incidence Rate (%)	Lower 95% Confidence Limit (%)
5	10	50.00	22.24
8	20	40.00	21.71
11	30	36.67	22.11
13	40	32.50	20.41
16	50	32.00	21.21
18	60	30.00	20.37

